3.2.3.2 Planned Follow-up for Discontinued Patients

Participants have the right to withdraw from the study at any time for any reason. A participant's withdrawal from the study will not jeopardize the relationship with their healthcare providers or affect their future care. This decision must be recorded in writing at the study site.

Should a participant decide to withdraw, all efforts will be made to complete and report the protocol defined study observations as completely as possible and to determine the reason for withdrawal.

3.3 INVESTIGATIONAL PRODUCT

3.3.1 Identity of Investigational Product: ¹⁸F-DCFPyL Injection

¹⁸F-DCFPyL Injection is an ¹⁸-Fluorine-labeled small molecule that targets the extracellular domain of PSMA. ¹⁸F-DCFPyL Injection is labeled with ['⁸F] fluorine that decays by positron (P+) emission to ['⁸0] oxygen and has a half-life of 109.77 minutes. The appearance of the ¹⁸F-DCFPyL Injection drug product is clear and free of visible particulate matters with a pH of 4.5-7.5. ¹⁸F-DCFPyL Injection is a sterile, clear particle-free solution supplied at a specific activity of at least 1000 mCi/μmol at the Time of Administration (TOA), and a radioactivity concentration (RAC) of 1-90 mCi/mL at the Time of Calibration (TOC). The TOC is at the end of synthesis (EOS). The recommended dose of ¹⁸F-DCFPyL is 9 mCi in a volume of :S 10 mL administered intravenously in a single injection. The chemical mass dose of carrier DCFPyL is less than 4 μg. The dosage range will be between 7 - 9 mCi.

3.3.2 Packaging and Labeling

Detailed information on the formulation, appearance preparation and labeling procedures can be found in the attached Investigator's Brochure and in the Package Insert provided by the manufacturer for the ¹⁸F-DCFPyL Injection.

3.3.3 Receiving, Storage, Dispensing, and Return

3.3.3.1 Receipt of Drug Supplies

The ¹⁸F-DCFPyL Injection product contains radioactive material and should only be handled by personnel trained and experienced in the use of radioactive isotopes with proper shielding and monitoring. Receipt and use are limited to a facility licensed by the Federal or State office for Radioactive Substances. Therefore, following release of the final drug product by the cGMP-compliant PET production facility, each unit-dose of ¹⁸F-DCFPyL Injection for intravenous injection will be delivered to the PET nuclear medicine laboratory at the respective investigational site.

3.3.3.2 Storage and Handling

Following receipt of the ¹⁸F-DCFPyL Injection product, qualified personnel will ensure that the study drug is delivered in good condition, inventoried, labeled, stored at room temperature, and administered by the labeled expiration time (10 hours from the EOS). ¹⁸F-DCFPyL Injection must not be diluted. The drug product contains radioactive material and should only be handled by personnel trained and experienced in the use of radioactive isotopes with proper shielding and monitoring.

3.3.3.3 Dispensing of Study Drug

The drug should be labeled and dispensed in compliance with the pharmacy manual, all regulatory agencies, and the investigator physician's prescription order. The 18F-DCFPyL dose will be measured by the qualified personnel in a dose calibrator prior to dispensing. Then, the syringe will be placed in a shielded carrier and administered as an intravenous injection. After the dose administration, the qualified personnel (nuclear medicine technologist) will re-assay the syringe for residual tracer activity. Measured radioactivity values and times of measurement will be documented, as well as the total injected volume. Regulatory agencies require the disposition of all investigational drugs received by each clinical site to be accurately accounted for. Information on drug disposition required by law consists of the date received, date dispensed, quantity dispensed, and the patient identification number to whom the drug was dispensed.

3.3.4 Administered Intervention

The dispensed dose will be injected slowly by a qualified nuclear medicine technologist as an IV injection. A dose of 9 mCi (333 MBq) or less ¹⁸F-DCFPyL injection will be administered via an in-dwelling catheter placed in an antecubital vein or an equivalent venous access. The drug product contains radioactive material and should only be handled by personnel trained and experienced in the use of radioactive isotopes with proper shielding and monitoring.

3.3.5 Selection of Dose in the Study

The intervention is a PET scan with the radiolabeled PSMA ligand ¹⁸F-DCFPyL. Prior to the first-in-human study with PyL (Study Jl418) at JHU, human dosimetry was extrapolated from a preclinical biodistribution study in xenograft mice.[55] The mouse organ activity concentrations in ³/₄ID/g were converted to the human %ID/organ by setting the ratio of organ ³/₄ID/g to whole-body ³/₄ID/gin the mouse equal to that in humans and then solving for the human %ID/organ. The adult male phantom organ masses listed in the OLINDA/EXM 1.0 were used for the conversion. The human source organ time-activity curves were fitted using a monoexponential function.

Because the biodistribution data were radioactive decay-corrected, only the biological removal constants were obtained from the curve fits, and the physical decay constant for F- was added in obtaining the time-integrated activity coefficients (TIAC). The source organ TIACs in MBq-h/MBq were entered in the OLINDA/EXM 1.0 for the dose calculations. The dynamic voiding bladder model was used to obtain the TIAC for the urinary bladder contents. The whole-body clearance half-life (obtained as the sum of sampled tissues, excluding the tumors) was used as the half-life to describe urinary bladder filling. All radioactivity was assumed to be eliminated via the urine. A one-hour voiding interval was assumed.

The estimated human organ exposure values are presented in Table 3. The urinary bladder wall was projected to be the organ with the highest absorbed dose. To limit the radiation-absorbed dose to the urinary bladder in accordance with 21 Code of Federal Regulations (CFR) § 361.1 (:S 50 mGy), the highest human dose is estimated to be 8.95 mCi. As a result,

the first-in-human dose used at JHU for obtaining basic information regarding the metabolism (including kinetics, distribution, and localization) was determined to be :S 9 mCi. The 9 mCi administered dose of ¹⁸F-DCFPyL Injection is comparable to the radiation dose of other radiotracers used in oncology such as [¹⁸F]-FDG.

3.3.6 Selection and Timing of Dose for Each Subject

This is an open-label study. All eligible patients will receive a single dose of the investigational agent. All patients will receive a single intravenous dose, 9 mCi (333 MBq) or less (range between 7 - 9 mCi) of ¹⁸F-DCFPyL Injection.

3.3.7 Procedures for Ensuring Subject Compliance

This is an open-label study. All eligible patients will receive a single dose of the investigational agent; therefore, no compliance measures are required.

3.3.8 Method of Assigning Subjects to Treatment Groups

This is an open-label study. All eligible patients will receive the investigational agent.

3.3.9 Investigational Product Accountability

3.3.9.1 Investigational Product Inventory Records

The Investigator or designee will verify the contents of each shipment against the shipping documents. Verification of receipt of investigational product will be documented according to the PI's requirements. An investigational product accountability log will be provided to the site for use by the Investigator to maintain current and accurate inventory records (batch, expiry, and quantity) covering the receipt, dispensing and the destruction of all investigational product.

3.3.9.2 Return or Destruction of Investigational Product

The Investigator is responsible for accounting for all unused study product and destroying all used study product containers in compliance with. At the conclusion of the study, or other situations as applicable (ex. site closure, IP expiry, etc.) the Investigator must agree to return or destroy all study materials as instructed by the package insert. Unused or residual waste should be disposed of as radioactive waste following the institution's standard operating procedures (SOPs) and/or applicable regulations or guidance.

3.3.10 Blinding

This study is a single-dose, open-label study. No blinding procedures will be used. No subjects will be blinded.

3.4 SCHEDULE OF STUDY ACTIVITIES

The time the imaging test will be performed relative to dosing is shown in the Schedule of Study Activities (Appendix A).

3.5 ASSESSMENT OF INTERVENTION

3.5.1 Imaging Protocol and Follow up

Patients will be intravenously injected with:::; 333 MBq (:::; 9 mCi) of radiotracer approximately 60 minutes prior to image acquisition and will be imaged using the GE Discovery PET-CT scanner at UPMC Hillman Cancer Center, UPMC Magee-Women's Hospital, or UPMC Shadyside Hospital. The scanner will be operated in three-dimensional (3D) emission mode on CT attenuation correction as the case may be and images will be reconstructed with manufacturer-supplied ordered subset expectation maximization iterative methods without point-spread function. The field of view for ¹⁸F-DCFPyL PET scans will be vertex to mid-thigh.

The PET images will be evaluated qualitatively by UPMC Hillman Cancer Center (HCC) nuclear medicine physicians. PET scans will be randomly assigned between five PET readers. Interpreters will have at least more than 5 years of PET interpretation and will interpret images. Double reading will be performed for all the PET scans. The readers will be provided with the recent PSA levels and the type of primary therapy (prostatectomy vs radiation therapy) but will be blinded to all other information. The report will indicate the localization of detected lesions either in the prostate bed, locoregional lymph nodes, distant lymph nodes, bones, and/or visceral organs. A scan will be deemed 'positive' if at least one lesion suggestive of disease recurrence is noted. Prostate lesions and lymph nodes will be considered positive if the uptake in those lesions exceeds blood pool activity. Bone lesions will be recorded as positive if the activity is higher than normal bone marrow uptake.

The UPMC HCC nuclear medicine physicians have extensive experience in interpreting FDG-PET/CT scans including those performed with a variety of agents currently used in the research setting. Scans will be interpreted using HE AW 3.2 Volume Viewer software package.

Visual interpretation:

1. Lymph nodes will be deemed positive if the PET scan uptake is focal and greater than blood pool (adjacent or mediastinal blood pool). Pelvic lymph nodes will be subclassified

- according to their localization as follows: R/L obturator, R/L external iliac, R/L internal iliac and other (total of 7 subgroups).
- 2. Visceral lesions will be considered positive if the uptake is focal and greater than physiologic background activity of the involvement organ or the anatomic location.
- 3. Bone lesions will be considered positive if the uptake is focal and greater than normal marrow uptake.
- 4. Prostate bed and prostate lesions will be considered positive if uptake is focal and greater than background activity of the prostate.

Follow-up imaging:

A chart review will be performed at 3, 6, 9 and 12 months with a plan to communicate with the referring oncologist team regarding the plan for follow-up imaging with a CT, MRI and/or bone scan. If a follow-up imaging is not obtained by 12 months, then imaging will be requested. Interpretation of follow-up imaging will be performed by local read. The follow-up conventional imaging should be the same modality/modalities as the initial staging work-up to allow for reproducible and accurate comparisons.

PET positive findings will be validated as true or false positive as outlined in more detail below. False negative ¹⁸F-DCFPyL PET findings cannot be determined as this would require biopsies of all PET negative lesions that are present on conventional imaging.

¹⁸F-DCFPyL PET validation will be based on follow-up imaging:

- 1. Lymph nodes will be assessed by change in size. PET positive lymph nodes will be considered:
 - a. True positive:
 - If on follow-up imaging within 3-12 months, lymph nodes seen on CT or MRI scan decrease by more than 30% (for patients undergoing systemic treatment of focal therapy at this site) or increase by more than 20% in short axis diameter (with a minimum of 3 mm in change in size).
 - If patients with solitary lymph node regions show a decrease of PSA by greater than 50% after targeted treatment (i.e. external beam radiation) and the lymph nodes do not change in size (less than 30% decrease or less than 20% increase in short axis diameter).

b. False positive:

• If on follow-up imaging within 3-12 months, sites of initial ¹⁸F-DCFPyL PET positive lymph node lesions seen on CT or MRI scan decrease by more than 30% without systemic therapy or focal therapy at this site.

- If PET positive lymph node lesions do not meet the criteria for above false positive or true positive findings.
- 2. Visceral lesions (non-lymph node soft tissue or organ) will be assessed by change in size. PET positive visceral lesions will be considered:
 - a. True positive:
 - If on follow-up imaging within 3-12 months, visceral lesions seen on CT or MRI scan decrease by 30% (for patients undergoing systemic treatment of focal therapy at this site) or increase by 20% in largest diameter.
 - If patients with solitary visceral metastasis show a decrease of PSA by greater than 50% after targeted treatment (i.e. external beam radiation) and lesions do not change in size (less than 30% decrease or 20% increase in largest diameter).

b. False positive:

- If on follow-up imaging within 3-12 months, sites of initial PET positive lesions seen on CT or MRI scan decrease by more than 30% without systemic therapy or focal therapy at this site.
- If ¹⁸F-DCFPyL PET positive lesions do not meet the criteria for above false positive or true positive findings.
- 3. ¹⁸F-DCFPyL PET positive bone lesions will be considered:
 - a. True positive:
 - If there was a corresponding positive sclerotic lesion on the CT portion of the ¹⁸F-DCFPyL PET in the same location as the focal uptake.
 - If there is focal uptake seen on the baseline bone scan performed within one month of ¹⁸F-DCFPyL PET.
 - If there is a lesion noted on the initial MRI imaging scan performed within one month of ¹⁸F-DCFPyL PET.
 - If within 12 months follow-up CT scan demonstrates development of sclerosis.
 - If within 12 months follow-up MRI scan demonstrates a new bone lesion.
 - If within 12 months follow-up bone scan demonstrates new focal uptake.

b. False positive:

- If ¹⁸F-DCFPyL PET positive bone lesions do not meet the criteria for true positive findings.
- 4. ¹⁸F-DCFPyL PET positive prostate bed and prostate lesions will be considered:
 - a. True positive:
 - If on follow-up imaging within 12 months, lesions seen on CT or MRI scan decrease by 30% (for patients undergoing systemic treatment of focal therapy at this site) or increase by 20% in largest diameter.

• If patients with prostate bed lesions show a decrease of PSA by greater than 50% after targeted treatment (i.e. external beam radiation) and lesions do not change in size (less than 30% decrease or 20% increase in largest diameter).

b. False positive:

- If on follow-up imaging within 3-12 months, sites of initial ¹⁸F-DCFPyL PET positive lesions seen on CT or **MRI** scan decrease by more than 30% without systemic therapy or focal therapy at this site.
- If ¹⁸F-DCFPyL PET positive lesions do not meet the criteria for above false positive or true positive findings.

Histopathology/Biopsy:

- 1. Localization of lesions for histopathology/biopsy will be classified according to the regions in table (Definition of regions) below.
- 2. The ¹⁸F-DCFPyL PET positive findings will be targeted to be confirmed by histopathology/biopsy if and whenever clinically feasible.
- 3. Histopathological procedures, biopsies and follow-up imaging will be performed as clinically indicated and as per the standard of care/institutional protocol. The following elective procedures may guide the investigator:
 - A. Positive HP/Biopsy: Confirmed sites of metastatic or tumor involvement by histopathology/biopsy will be discussed with the responsible physician/surgeon.
 - B. Negative Biopsy: Patients with suspected tumor recurrence on the PET with negative histopathology/biopsy will be handled as outlined below:

1. Lymph nodes:

- For patients undergoing nodal dissection: Patients will be rescanned with dedicated CT or MRI scan, if clinically feasible, to determine if the suspicious ¹⁸F-DCFPvL PET positive node was removed.
 - o If PET positive lymph node is still present, a repeat biopsy can be pursued if clinically feasible and applicable, or follow-up using imaging as described above will be performed.
 - o If the corresponding node was removed, then this will be considered a False Positive.
- For patients undergoing needle biopsy: Images of the procedure will be reviewed to determine if the correct node was biopsied.
 - o If the correct node was biopsied, then a negative biopsy will be considered a False Positive.
 - o If the incorrect node was biopsied, then follow-up imaging as described above will be performed if clinically feasible.

- 11. Bone lesions: Given the high rate of false negative biopsies for osseous metastases in patients with prostate cancer, patients with negative bone biopsies of PET positive lesions will be further evaluated:
 - If pathology demonstrates alternative diagnoses that is known to be PET positive (e.g. Renal Cell Carcinoma metastases, Paget's disease), then this will be considered a False Positive.
 - If pathology is indeterminate, then follow-up imaging as described above will be performed to determine if the lesion is a True Positive or False Positive.
- Additionally, a repeat ¹⁸F-DCFPyL PET may also be obtained as per treating physician discretion in addition to repeat conventional imaging (CT and/or MRI) in cases of negative biopsy to determine if the biopsy was true negative or false negative.
- C. Although not routinely performed during standard practice, immunohistochemical or specimens (primary and lymph node metastases) may be performed, although not required.

Table: Definition of regions

Region	Description
1	Prostate bed
2	Pelvis outside of prostate bed (including LNs)
3	Extra-pelvic soft tissue lesions, LNs, visceral metastases
4	Osseous metastases

3.5.2 Screening Assessments

Patients determined to meet the eligibility criteria to participate in the study will undergo Screening assessments as per the Study Schedule of Activities in Appendix A. The following screening procedures will be performed:

- Informed Consent will be obtained prior to any study-related procedures
- Eligibility assessment per the inclusion and exclusion criteria and diagnosis confirmation
- Subject demographics
- Prostate cancer history
- Vital Signs

- Physical examination, including height, weight, body mass index (BMI) and ECOG performance status assessment
- List of concomitant medications (hormonal agents only)
- Lab assessments

3.5.3 **Procedure for Registration of Subjects**

Patients must not start study activities prior to registration. Subjects can be enrolled after eligibility criteria are met. Registration will require the following information:

- Date of consent
- Participant's name
- Date of birth
- Primary study physician
- Confirmation of eligibility

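### The missing follow-up scan is requested only at 12 months, when every follow-up imaging criterion for a true positive closes, and the plan does not say how a later scan counts

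*Combined protocol and SAP*

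**What the plan says.** Section 3.5.1 schedules chart reviews at 3, 6, 9 and 12 months, each with contact about imaging plans. The only stated request for a scan is this: "If a follow-up imaging is not obtained by 12 months, then imaging will be requested".

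The same section then sets the validation rules:

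- **Nodes and viscera.** The size-change criteria run from 3 to 12 months: "If on follow-up imaging within 3-12 months, lymph nodes seen on CT or MRI scan decrease by more than 30" percent for nodes, and "If on follow-up imaging within 3-12 months, visceral lesions seen on CT or MRI scan decrease by 30" percent for viscera. Each has a 20% growth arm.
- **Prostate and prostate bed.** The size-change criterion has a limit of 12 months.
- **Bone.** Three follow-up criteria (CT, MRI, bone scan) have the same limit, for example "If within 12 months follow-up CT scan demonstrates development of sclerosis". Three further criteria use baseline imaging.
- **PSA route (nodes, viscera, prostate bed).** No time limit is stated. For nodes it needs a "decrease of PSA by greater than 50% after targeted treatment (i.e. external beam radiation) and the lymph nodes do not change in size".
- **Residual rule.** Whatever is left is FP. For nodes: "If PET positive lymph node lesions do not meet the criteria for above false positive or true positive findings". Viscera and prostate share the wording "PET positive lesions do not meet the criteria for above false positive or true positive findings", and bone has "PET positive bone lesions do not meet the criteria for true positive findings".

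Appendix A ends long-term follow-up at one year, and its footnote g puts the last chart review at 12 months. Section 3.10.1 says that the prespecified criteria govern validation, ranks histopathology above imaging and PSA, and speaks of validating findings in patients who have follow-up. Section 3.10.4 rules out imputation, apart from certain dates, and does not mention late scans.

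**The concern.** The request exists to obtain a verifying scan for a patient who has none. It is triggered by the absence of a scan at 12 months, which is also when the imaging criteria stop accepting scans. Unless the scan is done at the 12-month review itself, it arrives outside every window that could make it count as TP.

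The primary endpoint is at stake. If such lesions are counted FP, late verification is treated as evidence against the PET finding and PPV falls for a reason unrelated to the tracer. The per-region PPV is more exposed, because a TP lesion in another region does not help there. If the local investigators, who are unblinded under section 3.10.1, accept late scans informally, they are setting the window case by case.

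**Working it through.** **The plan's own figure.** 0.85 x 300 = 255 PET-positive patients. Clopper-Pearson 95% limits at n = 255 reproduce the table in section 3.10.2. For example, 204/255 gives 74.6% to 84.7% and 225/255 gives 83.6% to 91.9%. The widest interval for an observed PPV of 80% or more is 10.2 points, under the stated 12. The sample-size statement is not affected.

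**Rule check.** Take a PET-positive lesion without decisive pathology whose first follow-up scan is the requested one, done after month 12.

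| Rule in 3.5.1 | Node, visceral or prostate lesion that grew past 20% | Bone lesion with a new finding |
|---|---|---|
| Follow-up imaging TP | fails: window closed | fails: window closed (CT, MRI, bone scan) |
| PSA-response TP | fails: requires no size change | no such rule |
| Baseline imaging TP | no such rule | TP if met |
| FP by decrease without therapy | does not apply | no such rule |
| Residual rule | **FP** | **FP** unless a baseline criterion was met |

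A late scan can still support TP through the PSA route if the lesion was targeted, PSA fell by more than 50% and the size did not change. Bone has no growth criterion, so only new findings matter there.

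No tolerance is stated for any of the six windows. Appendix A does give one elsewhere: Day 7 carries plus or minus 2 days.

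**Size if counted FP.** One patient moved from TP to FP costs 1/255 = 0.39 points. Let f be the share of positives whose only route to TP is the late scan, and p the share of those that it would confirm. The loss is f x p, and the number moved is f x p x 255. Neither f nor p is in the documents; the values below are assumptions. As an illustrative start I take 217/255 = 85.1% (exact 95% CI 80.1% to 89.2%).

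| f | p | Loss f x p (points) | Moved f x p x 255 | PPV after rounding the number moved |
|---|---|---|---|---|
| 2% | 85% | 1.7 | 4.3, about 4 | 213/255 = 83.5% |
| 5% | 85% | 4.3 | 10.8, about 11 | 206/255 = 80.8% |
| 10% | 85% | 8.5 | 21.7, about 22 | 195/255 = 76.5% |
| 2% | 40% | 0.8 | 2.0, about 2 | 215/255 = 84.3% |
| 5% | 40% | 2.0 | 5.1, about 5 | 212/255 = 83.1% |
| 10% | 40% | 4.0 | 10.2, about 10 | 207/255 = 81.2% |

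The lower arm of the starting interval is 5.0 points. Matching it takes 13 moved patients (204/255 = 80.0%, a shift of 5.1 points). That needs f = 13/(0.85 x 255) = 6.0%, or f = 13/(0.40 x 255) = 12.7%.

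**Size if excluded.** With p = 85%, dropping 5, 13 or 26 late patients, of whom 4, 11 or 22 would be confirmed, gives 213/250 = 85.2%, 206/242 = 85.1% and 195/229 = 85.2%. PPV hardly moves. With p = 40% and f = 10% it rises, to 207/229 = 90.4%, because the unconfirmed patients leave the denominator too.

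**The case against.** The strongest reply is that FP is not the only available reading. Section 3.10.1 validates findings in patients with follow-up, and section 3.10.4 does not impute. A sponsor could say that a patient with no scan inside the window lacks qualifying follow-up and belongs outside TP + FP. This stands as a second reading. It does not settle the matter: a patient scanned at month 13 does have follow-up, section 3.5.1 has no not-evaluable class, and the residual rule has no time limit.

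It can also be said that the scan ordered at the fourth chart review was meant as the 12-month scan. That is plausible, but the text does not say so.

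The limits on reach also stand. Reviews at 3, 6 and 9 months should prompt earlier imaging, histopathology ranks first and has no window, and one other TP lesion is enough for the per-patient endpoint.

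A reader might infer that every lesion that progresses on a requested scan becomes FP, or that PPV is certain to be several points too low. The exceptions and the second reading rule out the first. The absence of any figure for late scans rules out the second. The prior phase 3 trial summarized in section 1.1 had 24 to 33 unevaluable patients among 123 to 137 positives per reader. These cannot stand in for late scans, since the footnote attributes them to an unsubmitted reference standard or a lesion-level false negative.

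**Conclusion.** The mismatch between the request and the windows is in the text, and it bears on the primary and secondary endpoints. The direction of its effect is less certain. On the literal FP reading PPV is lowered. On the exclusion reading it is almost unchanged if late patients resemble the rest, and raised if they are confirmed less often. The plan does not choose.

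The 0.39 points per patient is firm given 255 positives. The range of 0.8 to 8.5 points rests wholly on assumed f from 2% to 10% and p of 40% or 85%, and the true number may be small. The point should be fixed because the rule is unclear on the primary endpoint and cheap to repair, not because a large bias has been shown.

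**What to change.** Before validation begins:

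1. State in section 3.5.1 that a scan requested at the 12-month review, and done within a tolerance fixed in advance, is judged by the existing TP and FP criteria. Extend the follow-up period in Appendix A to match.
2. State that a lesion with no scan inside the extended window and no other validation route is not validated. Report it separately; do not count it FP by default.
3. Report how many patients were classified on a scan after 12 months. Give two sensitivity PPVs: late-scan patients excluded, and late-scan patients counted FP.

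The cost is a few sentences, one schedule edit, slightly longer data collection and two small analyses. PET acquisition and enrollment do not change. Moving the request earlier would also close the gap, but it leaves lesions less time to reach 20% growth, so slow-growing disease could reach the residual FP rule more often. If the sponsor prefers that route, the protocol should say so.

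### The follow-up imaging request depends on whether any scan exists by month 12, not on whether a scan exists that can classify each PET-positive lesion

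*Combined protocol and SAP*

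**What the plan says.** Under Follow-up imaging in section 3.5.1, "A chart review will be performed at 3, 6, 9 and 12 months with a plan to communicate with the referring oncologist team"; the subject of that contact is which conventional scans (CT, MRI, bone scan) are planned. The request follows: "If a follow-up imaging is not obtained by 12 months, then imaging will be requested". On modality, the section adds: "The follow-up conventional imaging should be the same modality/modalities as the initial staging work-up to allow for reproducible and accurate comparisons". Appendix A places conventional imaging in long-term follow-up, from day 8 to one year, and its footnote accepts a dedicated CT, MRI and/or bone scan.

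The validation criteria in the same section are narrower. For nodes the size criterion begins "If on follow-up imaging within 3-12 months, lymph nodes seen on CT or MRI scan decrease by more than 30" per cent, and for visceral lesions "If on follow-up imaging within 3-12 months, visceral lesions seen on CT or MRI scan decrease by 30" per cent. Prostate and prostate-bed lesions also need a size change on CT or MRI, but the true-positive criterion says only within 12 months. Bone lesions can be confirmed from baseline CT, bone scan or MRI, or by follow-up with any of the three, for example "If within 12 months follow-up CT scan demonstrates development of sclerosis".

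Each lesion class ends with a residual rule that yields a false positive. For nodes it reads "If PET positive lymph node lesions do not meet the criteria for above false positive or true positive findings". Section 3.5.1 has no unevaluable category. Section 3.10.1 makes everyone scanned evaluable but validates positive findings only in patients with follow-up, a term it does not define. Section 3.10.4 rules out imputation apart from certain dates.

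**The concern.** The event that triggers a request and the event that allows classification are defined differently. A scan can count as follow-up obtained and still be unable, under the protocol's own criteria, to confirm the lesion. Such a lesion is scored false positive because of when or how the patient was imaged in routine care, not because of his disease status.

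This feeds directly into the primary endpoint, TP/(TP + FP) per patient, and into the per-region secondary endpoint. The affected men are unlikely to be a random subset: section 3.5.1 leaves biopsy and follow-up imaging to clinical indication, so the timing and type of scan plausibly follow the treating team's plan, although the documents give no figure on this. A measurement not taken inside its window cannot be recovered at analysis.

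**Working it through.** **Trigger against criteria (section 3.5.1 and Appendix A)**

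| Lesion class | Follow-up scan that can confirm | True-positive window | Other routes to true positive |
|---|---|---|---|
| Node | CT or MRI | 3–12 months | Histology; PSA fall if nodal disease is solitary |
| Visceral | CT or MRI | 3–12 months | Histology; PSA fall if metastasis is solitary |
| Prostate/prostate bed | CT or MRI | Within 12 months | Histology; PSA fall (prostate bed) |
| Bone | CT, MRI or bone scan | Within 12 months | Histology; baseline CT, bone scan or MRI |

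The PSA routes require targeted treatment and also an unchanged lesion size, so they too need a measurement, though those bullets state no window for it.

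Four cases follow.

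- PET-positive node, only scan a CT at month 2: it is follow-up imaging within day 8 to one year, so no request is required. It lies outside the 3–12 month window, so the residual bullet applies.
- PET-positive node, visceral or prostate-bed lesion, only scan a bone scan at month 8: no request is required and no size can be measured, so the residual bullet applies.
- PET-positive bone lesion, CT at month 2: the scan is inside the bone window and counts for both purposes. There is no gap.
- No scan by month 12: the request fires, but the scan falls at or after month 12 and mostly misses every window.

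**The plan's own figures (section 3.10.2)**

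300 × 0.85 = 255 expected positive patients. Clopper-Pearson 95% intervals at n = 255: 204/255 gives 74.6–84.7% (plan: 75–85%) and 214/255 gives 78.8–88.2% (plan: 79–88%). The remaining rows also reproduce, the 88% row with 225/255. Near 85%, 217/255 gives 80.1–89.2%, a width of 9.1 points and a half-width of about 4.5.

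**Size under an assumed rate**

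Let x be the share of true-positive patients whose only obstacle is the lack of a qualifying scan, with no histology, PSA route, baseline bone confirmation or other confirmed lesion. Then reported PPV = 0.85 × (1 − x):

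- x = 2%: 0.85 × 0.98 = 83.3%, a loss of 1.7 points
- x = 5%: 0.85 × 0.95 = 80.8%, a loss of 4.2 points
- x = 10%: 0.85 × 0.90 = 76.5%, a loss of 8.5 points

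One affected patient moves PPV by 1/255 = 0.4 points.

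**How the handling rule changes the answer**

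Now let u be the share of all 255 positive patients without a usable reference, with PPV 85% among the rest, in whole patients.

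| u | Patients | Counted FP (95% CI) | Excluded (95% CI) | Counted TP |
|---|---|---|---|---|
| 2% | 5 | 212/255 = 83.1% (78.0–87.5) | 212/250 = 84.8% (79.7–89.0) | 217/255 = 85.1% |
| 5% | 13 | 206/255 = 80.8% (75.4–85.4) | 206/242 = 85.1% (80.0–89.4) | 219/255 = 85.9% |
| 10% | 26 | 195/255 = 76.5% (70.8–81.5) | 195/229 = 85.2% (79.9–89.5) | 221/255 = 86.7% |

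Exclusion costs little precision: at u = 10% the interval is 9.6 points wide, against 9.1 with nobody unevaluable.

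**An outer illustration from the documents**

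In the earlier phase 3 study of this tracer, tabulated in section 1.1, 33/137, 24/124 and 24/123 positive scans by reader (24.1%, 19.4%, 19.5%) were unevaluable and left out of the denominator. Counting them as false positives would turn 85.6%, 87.0% and 84.8% into 89/137 = 65.0%, 87/124 = 70.2% and 84/123 = 68.3%.

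**The case against.** The strongest objection is that the request, even when it fires, comes too late: asking at month 12 yields a scan mostly outside the window, so a request that never fires costs little by itself. This stands. Tightening the definition of an adequate scan would achieve little unless the check also moves earlier, and the residual rule with no unevaluable category is the deeper cause.

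The text is also silent rather than explicit. A reader might infer that any scan cancels further imaging, but no sentence says so. The quarterly chart reviews, with their planned contact with the referring team, and the same-modality sentence give partial protection. They do not close the gap: no adequacy check is defined at the reviews, and the modality sentence is advisory and follows the initial staging work-up rather than the PET-positive lesion.

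A reader might infer that every scan before month 3 is unusable. The true-positive criteria do not support that: the 3-month floor applies to nodes and visceral lesions only. For prostate and prostate-bed lesions it appears only in the explicit false-positive bullet, and for bone not at all.

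Finally, the false-positive default is not fully settled. Section 3.10.1 could be read as leaving men without adequate follow-up unvalidated. But a man with one unusable scan may count as followed up, and section 3.5.1 then scores him false positive.

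**Conclusion.** The gap is real and worth closing before data collection. Read literally, the plan allows a scan that cannot classify a lesion to satisfy the follow-up step, and the residual rule then makes the lesion a false positive unless histology or a PSA route applies. Through this mechanism PPV can only fall. Per-region PPV is more exposed, because a patient with another confirmed lesion probably still counts as true positive, although the lesion-to-patient rule is not stated.

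The size is unknown. The 2–10% range is an assumption, and it holds only for men with no other route to confirmation. Within it, the loss at 5% is already close to the half-width of the planned interval.

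Two stronger conclusions are not supported. A reader might infer that the trial's PPV will be biased down overall, but the documents do not determine the net bias of the composite reference standard. A reader might also carry over the 19–24% unevaluable share from the earlier phase 3 study, but that share covers any reason for lacking a usable reference, so it is an upper illustration and not an estimate for this trial.

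**What to change.** Replace the month-12 trigger in section 3.5.1 with a lesion-specific rule along these lines:

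- At the 9-month chart review, take each PET-positive lesion not already classified by histology or by the baseline bone criteria. Check whether a scan of a modality named in that lesion's own criteria exists within its own window: CT or MRI at 3–12 months for node and visceral lesions; CT or MRI within 12 months for prostate and prostate bed; CT, MRI or bone scan within 12 months for bone.
- If no such scan exists, request one then, so that it falls inside the window.
- A scan outside a lesion's own window or modality list does not count as follow-up obtained for that lesion. Apply no general month-3 exclusion, since that would conflict with the bone and prostate-bed true-positive criteria.
- Classify lesions still without a qualifying scan or other reference as unevaluable, not false positive. Align the residual bullets and section 3.10.1 with this.
- In section 3.10.3, report PPV with unevaluable cases excluded and, as sensitivity analyses, with all counted false positive and all counted true positive.

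The cost is protocol wording and a modest number of extra requests at month 9 for conventional imaging of a kind the protocol already includes.
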